6.0 Study Design and Procedures

[figure not shown]
Participants. The sample size for the present study is 80 adults, ages 18-65 years old. However, to account for potential screen-fails, participants requesting to drop out of the study, and the PI withdrawing participants due to meeting termination criteria, approval for 120 participants is requested. Exclusion criteria are listed above. We will recruit

individuals who meet DSM-5 criteria for moderate or severe AUD. As noted above, we will not include individuals who meet DSM-5 diagnostic criteria for current or lifetime MDD, OCD, bipolar disorder, or psychotic disorder. All other lifetime psychiatric diagnoses will be assessed and examined as potential covariates in analyses. Individuals younger than age 18 will be excluded because suvorexant is not FDA-approved for use in children. Individuals older than 65 will be excluded to minimize the potential for adverse medication side-effects and prescription drug interactions. Limiting the sample to adults younger than 65 also reduces potential heterogeneity in brain structure and function, and psychophysiological stress reactivity, which could confound data interpretation in the current sample size.

Recruitment. Adults will be recruited via print advertisements, word-of-mouth referrals (including through the OSU ED), and internet postings (e.g., craigslist, social media sites). We expect to recruit all participants within 2 years, consistent with our prior psychophysiological and pharmacological challenge studies.

Entry Assessments. Inclusion/exclusion criteria. Potential participants will be screened using structured questionnaires (see Table 1 and Table 2). Exclusionary criteria will be those that would interfere with interpretation of brain and/or behavioral findings or increase risk of side effects/adverse events - see above for a complete list. After consent, if interested participants meet eligibility criteria, and are able to provide consent, they will be enrolled in the study.

Figure 1.

Study Overview. The study is a double-blind, between-subjects, randomized clinical trial with a multi-session lab paradigm (see Figure 1). Participants will first complete an initial Screening Session where they will complete an assessment of study eligibility (described above), a clinical interview, and questionnaires. If participants are found to be eligible, they will be randomized to a treatment group (SUV or placebo) and protocol arm (BEHAVIOR or BRAINS Group). Those in the BEHAVIOR Group will complete electromyography (EMG)/electroencephalography (EEG) only and those in the BRAINS Group will complete EMG/EEG + fMRI.

Therefore, participants have a chance of being randomized to four different groups (20 participants/group): 1) BEHAVIOR - SUV; 2) BEHAVIOR - Placebo; 3) BRAINS - SUV; and 4) BRAINS - Placebo.

BEHAVIOR Group Overview:

Following the Screening Session, participants randomized to the BEHAVIOR group will come in-person to Lab Visit 1 where they will complete the psychophysiological stress paradigm and Alcohol Cue Reactivity EEG task. Days later, they will return to the lab for Visit 2 (Acute Drug Challenge) and repeat the protocol during their first dose of medication (placebo or 10mg SUV). Next, they will be instructed to take a 10mg dose of SUV (or placebo) each night before bed for 4-weeks. Daily online assessments of medication compliance, side-effects, alcohol use, mood, and sleep will be collected. During the final week of the protocol subjects will return for Lab Visit 3 to repeat the paradigm (dose taken night prior, as prescribed).

BRAINS Group Overview:

Following the Screening Session, participants randomized to BRAINS Group will complete the same procedures as above with the exception of completing two additional fMRI visits pre- and post-treatment. Therefore, participants will complete: Lab Visit 1 (EMG/EEG), Lab Visit 2 (fMRI), Lab Visit 3 (Acute Drug Challenge), four weeks of SUV (or placebo) administration with daily online assessments, Lab Visit 4 (EMG/EEG), and Lab Visit 5 (fMRI).

Screening. During the Screening Session, participants will complete an assessment of study eligibility, the Structured Clinical Interview for DSM-5 (SCID-5)³¹ with trained study staff, and a short battery of self-report questionnaires (see Table 1 and Table 2). Participants will be given the choice to complete the Screening Session online or in-person to accommodate potential limited access to the internet.

Measures of Alcohol and Other Substance Use: (1) Alcohol Use Disorders Identification Test (AUDIT)³², (2) Timeline Follow-back (TLFB)³⁰; (3) The Obsessive Compulsive Drinking Scale (OCDS)³³, (4) The Drinker Inventory of Consequences (Dr-InC)³⁴, (5) the CIWA-Ar²⁹, (6) Drinking Motives Questionnaire-Revised (DMQ-R)³⁵, (7) Drug Abuse Screening Test (DAST)³⁶, (8) Cannabis Use Disorder Identification Test (CUDIT)³⁷, and (9) the Fagerstrom Test for Nicotine Dependence (FTND)³⁸.

Measures of Psychiatric Symptoms and Personality: (1) Beck Depression Inventory (BDI-II)³⁹, (2) Beck Anxiety Inventory (BAI)⁴⁰, (3) Generalized Anxiety Disorder Questionnaire (GAD-7)⁴¹, (4) Beck Hopelessness Scale⁴², (5) Snaith-Hamilton Pleasure Scale (SHAPS)⁴³, (6) PTSD Checklist-Civilian Version (PCL-5)⁴⁴, (7) Life Events Checklist for DSM-5 (LEC-5)⁴⁵, (8) The Personality Inventory

for DSM-5 (PID-5)⁴⁶, and (9) Beck's Scale for Suicidal Ideation Lifetime (SSI)⁴⁷, (10) The Depression, Anxiety and Stress Scale (DASS-21)⁴⁸, (11) The Inventory of Depression and Anxiety Symptoms (IDAS-II)⁴⁹, (12) Childhood Trauma Questionnaire (CTQ)⁵⁰, (13) Anxiety Sensitivity Index (ASI), (14) Highly Sensitive Person Questionnaire (HSP).

Other Measures: (1) Pittsburg Sleep Quality Index (PSQI)⁵¹, (2) Health Questionnaire, (3) Demographic Questionnaire, (4) Intolerance of Uncertainty (IUS)⁵², (5) Contact Information Form, (6) Emotion Regulation Questionnaire (ERQ)⁵³, (7) Psychiatric Treatment History Form (clinician administered), (8) Medication History form (clinician administered); (9) Exclusionary Medication Checklist; (10) BMI Questionnaire.

Identifying and Monitoring Drug-Drug Interactions. The study physician will review the participant's self-report Health Questionnaire, self-report Exclusionary Medication Checklist, and clinician administered Medication History form prior to randomization in order to assess exclusionary criteria and identify potential drug-drug interactions. PI and the study physician will utilize Lexicomp to check drug-drug interactions and only interactions of minor severity will be allowed. Those found to have potential moderate or severe drug-drug interactions will be withdrawn from the study, consistent with study exclusionary criteria. Potential drug-drug interactions will continually be monitored throughout the duration of the study.

Randomization, Blinding, and Dosing. A computerized stratified block randomization will assign subjects to a treatment group and protocol arm. The randomization will be stratified by biological sex. The research team and participants will be blind to medication assignment. The PI will have the ability to unblind if needed. OSU Investigational Drug Services (IDS) staff and CRC medical staff will be unblinded.

Participants will receive either placebo or suvorexant (Belsomra®; 10mg; Merck & Co). This dose was chosen because it is the lowest clinical dose for sleep and arousal-related outcomes. We used 10mg in our pilot project and found significant change in reactivity to U-threat without adverse reactions (Protocol#: 2020H0285).

Laboratory Tasks. Participants will complete a startle response to threat task at the EMG/EEG, fMRI, and Acute Drug Challenge Visits (described below). The same paradigm will be administered during the EMG/EEG and Acute Drug Challenge Visit. The fMRI task is analogous to the original design; however, shock is administered to the left foot to minimize potential scanner interference and individual shock levels are re-calibrated. During the tasks, we will collect psychophysiological measures including startle eyeblink potentiation. At the EMG/EEG visit a second task, Alcohol Cue Reactivity⁷¹ will be completed. These tasks are well-established, validated paradigms,

previously used in our laboratory for the past several years in both healthy and adults with AUD.

EMG/EEG Lab Visits. Task 1: Startle response to threat. Consistent with prior studies^{54,55}, participants will first complete a brief habituation task to prevent early exaggerated startle responding, during which a series of acoustic startle probes will be administered. For the threat task itself, a brief, mild electric shock will be used to elicit aversive responding. Importantly, the current shock equipment and shock protocol has previously been used in our laboratory. Prior to the task, shock electrodes will be placed on the participants' left wrist, followed by a shock work-up procedure in which they will receive increasing levels of shock intensity (max. = 5 mA) until they reach a level that they describe as feeling "highly annoying but not painful." Shock level will be determined ideographically to ensure equality in perceived shock aversiveness. The task itself includes three within-subjects conditions – no shock (N), predictable shock (P), and unpredictable shock (U). Text at the bottom of the screen informs participants of the current condition. Conditions last 145-s, during which a 4-s visual countdown (CD) is presented six times. The interstimulus intervals (ISIs) range from 15 to 21-s during which only the text of the condition is on the screen. No shocks are delivered during the N condition. A shock is delivered every time the CD reaches 1 during the P condition. Shocks are delivered at random during the U condition. Startle probes are administered during both the CD and ISI. Each condition is presented two times in a randomized order. Participants receive 24 shocks (12 in P; 12 in U) and 60 startle probes (20/condition). This task will be conducted during all three EMG visits, including the Acute Drug Challenge Visit.

Startle Data Collection and Processing. Via Presentation software (Albany, CA), acoustic startle probes that are 40-ms duration, 103-dB bursts of white noise will be presented. Electric shocks will last 400-ms. Startle will be recorded using the PI's BioSemi Active Two system (BioSemi, Amsterdam, The Netherlands) and data collected and processed (e.g., filtering, rectification, smoothing, scoring blinks) according to published guidelines, as reported in the PI's publications⁵⁶⁻⁵⁸. Startle is processed using the PI's interactive 'batch' program in BrainVision Analyzer 2 (Brain Products). Consistent with the PI's work, and published recommendations⁵⁹, we will calculate standardized residual scores for the two forms of threat anticipation - U-threat and P-threat. This method has been shown to most accurately quantify the difference between threat and no-threat reactivity. Blinks will be scored as missing if the baseline period was contaminated with noise, movement artifact, or if a spontaneous or voluntary blink began before minimal onset latency. For each task, mean blink magnitude scores for each condition (N, P, U) will be calculated and used in primary analyses.

EMG/EEG Visits. Task 2: Alcohol Cue Reactivity. Participants will complete a modified Alcohol Cue Reactivity Task⁷¹. The task consists of four conditions: alcoholic

Condition	CD	ISI	CD	ISI
No-Shock (N)	321 No Shock	321 No Shock	321 No Shock	321 No Shock
Predictable Shock (P)	321⚡ Shock at 1	321⚡ Shock at 1	321⚡ Shock at 1	321⚡ Shock at 1
Unpredictable Shock (U)	321⚡ Shock Anytime	321⚡ Shock Anytime	321⚡ Shock Anytime	321⚡ Shock Anytime

beverages, non-alcoholic beverages, pixilated control images, and fixation (rest) periods. Each of the 4 conditions consists of 22 stimuli each presented four times. Stimuli are presented sequentially in a pseudo-randomized order each for about 1 second with a 1250 ms inter-stimulus interval. Alcohol and non-alcohol beverage stimuli were previously standardized to ascertain adequate identification, and comparable valence, arousal, and visual characteristics between the two conditions⁷¹. Throughout the task, participants will be instructed to indicate their mood and the valence of the different stimuli.

Psychophysiology Data Collection and Processing. During the Alcohol Cue Reactivity task we will record continuous electroencephalography (EEG) readings using a 32 channel ActiveTwo BioSemi system (BioSemi, Amsterdam, Netherlands). The data is recorded off the scalp, non-invasively, while participants are wearing a stretch lycra EEG cap. The EEG signal will be pre-amplified at the electrode to improve the signal-to-noise ratio. The data will be digitized at 24-bit resolution with a Least Significant Bit (LSB) value of 31.25nV and a sampling rate of 1024Hz, using a low-pass fifth order sinc filter with a -3dB cutoff point at 204.8Hz. Off-line analysis will be performed using Brain Vision Analyzer software (Brain Products), using conventional preprocessing steps. Data will be re-referenced to the average of the two mastoids and high-pass (0.1Hz) and low-pass (30Hz) filtered. Data will be segmented around event markers that correspond to the administration of task stimuli. Baseline correction for each trial will be performed and brain activity averages will be computed for each condition, for each task.

fMRI Data Collection. All scanning will be performed at the OSU Center for Cognitive and Behavioral Brain Imaging (CCBBI), using a Siemens 3T Prisma MR scanner with Total Imaging Matrix (TIM) system and a phase-array head coil for parallel imaging to minimize signal loss and image distortion. Prior to entering the fMRI scan, female participants will complete a urine pregnancy test. Each session will begin with an MP-RAGE high-resolution structural imaging of the whole brain (TI = 950 ms; TR = 1950 ms; TE = 4.44 ms; flip angle 120; 176 sagittal slices; 256 x 256 matrix size with spatial resolution as 1x1x1mm³, slice partial Fourier of 6/8). fMRI signal measures will be acquired using a T2*-weighted Echo-Planar Imaging sequence with BOLD contrast to measure task-related effects, optimized to reduce susceptibility artifact in the ventral frontal cortex and medial temporal lobe (TR = 2000 ms; TE = 25 ms; flip angle =70o; 64 x 64 in-plane resolution; and 1906 Hz/pixel bandwidth). Thirty-five 3 mm axial slices will be acquired to cover the cerebrum and most of the cerebellum with no gap. Slices will be tilted about 20o clockwise along the AC-PC plane to obtain better signal in the orbitofrontal cortex. These parameters are used to minimize signal dropout, image distortion and susceptibility artifacts. Head movement is minimized through instruction, eye-tracking, and foam padding within the head coil. Participants will complete 2 tasks and spend 45 minutes in the bore of the magnet.

fMRI Lab Visits - Task 1: Startle response to threat. Stress reactivity will be probed using an fMRI version of the NPU threat paradigm, developed

N	4	3	2	1	
	No Shock	No Shock	No Shock	No Shock	END OF TRIAL
P	4	3	2	1	
	Shock at 1	Shock at 1	Shock at 1	Shock at 1	END OF TRIAL
U	6	5	4	3	
	Shock Anytime	Shock Anytime	Shock Anytime	Shock Anytime	END OF TRIAL

and implemented by the PI⁶⁰. The fMRI task is analogous to the original NPU design; however, shock is administered to the left foot to avoid scanner interference. Individual shock levels are re-calibrated.

The task uses threat-of-mild-electric-shock to elicit stress in two contexts: threat of a predictable electric shock (fear) and threat of an unpredictable electric shock (anticipatory anxiety). Shock level is determined ideographically using a pre-task shock work-up in which participants receive increasing levels of shock intensity (max 5mA) until they reach a level they describe as “highly annoying but not painful.” The task includes three within-subjects conditions: no-threat (N), predictable threat (P), and unpredictable threat (U). Text at the bottom of the screen informs participants of the current task condition. Each condition includes a countdown (CD) that ranges 3-8s (M=5s). During N, no shocks are delivered. During P, a shock is delivered when the CD reaches “1”. During U, shocks are delivered at random. Following each CD there is a fixation for 5-7s (M= 6s). N, P and U CDs are presented in blocks of 5 and each condition/block is administered in a randomized order 5 times over two runs for a total task time of 10 mins. Participants receive 20 shocks (10 in P, 10 in U) during each run. Electric shocks will last 400-ms. The rate of “Shock at 1” during the P condition is 60% to prevent an excessive number of total shocks during the task, consistent with the NPU version used by Grillon and colleagues⁶¹. Acoustic white noise startle probes that are 103bd, 40-ms duration will be administered via headphones during the NPU threat paradigm. Startle data is collected from two peripheral electrodes placed under the participant's left eye and recorded using Brain Vision Recorder software. Our data from two studies indicate that despite being shocked, participants are able to remain still and total motion is minimal (n=237; M translation=.03±.02mm and rotation=.02±.01degrees). PI [name]'s lab is currently recording simultaneous fMRI+startle in another IRB approved study (Protocol#: 2021H0039). After the task, self-report ratings of the threat, consistent with above, will be assessed.

During the NPU task, BOLD is the index of stress reactivity. The BOLD contrasts of interest will capture activation during threat anticipation: U-threat anticipation > No-threat anticipation and P-threat anticipation > No-threat anticipation. At the end of the task, participants rate how intense, arousing, and anxiety provoking the conditions and shocks were. Of note, our prelim data from two separate studies indicate that despite being shocked, participants are able to remain still and total motion is minimal (n=237; M age=19.3; M translation=.03±.02mm and rotation=.02±.01degree across runs).

fMRI Lab Visits - Task 2: The Resting State Task (RST). For this task participants will view a fixation cross on a blank background for approximately 10 minutes. Participants will be instructed to keep their eyes open and focused on the cross, and to try not to think of anything in particular.

fMRI Data Processing. Data preprocessing will involve well-tested, routine procedures used in our lab. Conventional steps (e.g., realignment, normalization, smoothing) will be executed using Statistical Parametric Mapping software (SPM8; Wellcome Trust Center for Neuroimaging, London). Strict quality control procedures will be in place to evaluate head motion (e.g., excluding subjects with >1.5 mm movement in any direction) and ensure proper normalization. Motion parameters will be included in all

first-level models as regressors of no interest. Statistical analyses will use the modified General Linear Model (GLM) in combination with a temporal convolution for block-related analyses in a random effects model. Statistical inference will use random field theory to account for non-independent observations within a smooth map. We will implement 2 complementary approaches to test regional activation: 1) hypothesis-driven region-of-interest (ROI)-based analysis of BOLD percent signal change (PCS) created from anatomy-based landmarks using small-volume correction ($p < .05$, FWE-corrected); and 2) whole-brain activation search at a threshold of $p < .05$ (FWE-corrected).

Suvorexant Accountability and Compliance. The compound pharmacy will prepare the study capsules and supply them to OSU Investigational Drug Services (IDS). Appropriate storage temperature of suvorexant will be maintained by IDS. IDS staff will maintain records of distribution to each subject. These records will include dates, quantities, batch, expiration dates, and unique code numbers assigned to the product and study subjects. Prior to distribution, the IDS will prepare each subject's study medication in blister packaging. Each blister is clearly marked with the date the capsule will be ingested.

Administration of Drug or Placebo (Acute Drug Challenge).

Overview. Following the initial EMG/EEG or fMRI visit (dependent upon randomization) participants will return to the lab for the Acute Drug Challenge Visit. Participants will first arrive to the Clinical Research Center (CRC) for drug or placebo administration. After 2-hours, participants will then be escorted to the PI's laboratory for the EMG assessment. After the assessment, participants will return to the CRC for further monitoring and discharge to assure that vital signs (heart rate, oximetry, blood pressure) are within normal limits and/or do not require immediate medical attention and that the participant can maintain wakefulness as demonstrated by a score of 7 or less on the Karolinska Sleepiness Scale (KSS)⁶² (1="Very alert"; 5="Neither alert nor sleepy"; 7="Sleepy, but no difficulty remaining awake; 9="Very sleepy, fighting sleep"). Participants will consent to not operating a vehicle for at least 24 hours after the Acute Drug Challenge Visit. A taxi voucher or Uber reservation will be provided by study staff for transportation home if participants do not have a means to transportation.

Placebo and suvorexant (i.e., Belsomra®; 10mg; Merck & Co., Inc.) will be obtained from the compound pharmacy and will be placed in opaque capsules with dextrose filler for each session. Placebo capsules will be identical in appearance but will contain only dextrose. All capsules will be administered to subjects in double-blind conditions at the CRC under medical supervision.

Administration Timing. Peak plasma concentration for suvorexant is 2 hours post-ingestion. Therefore, participants will receive the drug (or placebo) at the CRC upon arrival. After 1.5 hours (90 minutes post ingestion), participants will be escorted to the laboratory for EMG/EEG testing. Laboratory assessments will occur during peak concentration, ~2 hours post-ingestion.

Self-Report Assessments During Acute Drug Challenge. Throughout the Acute Drug Challenge Visit standardized questionnaires will be used to assess mood states and subjective drug effects: (1) Karolinska Sleepiness Scale (KSS)⁶²; (2) Anxiety Visual Analog Scales (VAS)⁶³; and (3) Drug Effects Questionnaire (DEQ)⁶⁴; and Profile of Mood

States (POMS)⁶⁵. The KSS, VAS and DEQ will be collected immediately before capsule ingestion (Time 0), and approximately 30, 60, 90, 120, 150, 180, and 210, and 240 minutes afterwards. The POMS will be completed immediately prior to capsule ingestion (Time 0), and approximately 60 minutes, 120 minutes, and 240 minutes afterwards.

Vitals Signs Measurements During Acute Drug Challenge. Physiologic measures will be collected throughout the study visit: (1) Blood Oxygen (O₂) Saturation; (2) Heart Rate and (3) Blood Pressure will be taken before capsule ingestion (Time 0), and approximately 30, 60, 90, 120, 150, 180, and 210, and 240 minutes afterwards. Measurements will be performed at the CRC or in the PI's lab using portable blood pressure and finger oximeter. Measurements will be obtained using a finger oximeter and portable blood pressure cuff. Any participant who experiences excessive drowsiness, allergy symptoms, and/or adverse drug reactions will be assessed by the CRC and study physician and immediately withdrawn from the study as a safety measure.

Drug Trial and Monitoring. At the end of the acute challenge, subjects will be provided the rest of their prescription (SUV or placebo) in blister packaging, prepared by OSU IDS. The blister packaging will be labeled with each date of the protocol. Subjects will be directed to ingest one pill each night, as they get into bed (~30 mins prior to sleep time) to mitigate drowsiness, consistent with SUV's prescription.

Each morning for the 4-week medication trial period, subjects will be asked to complete a brief clinical assessment, sent directly to subjects' smartphones at 8:30am. The survey will capture: medication adherence (yes/no); timing of pill ingestion; time spent in bed and asleep; medication side-effects; number and timing of alcoholic beverages; alcohol craving; illicit substance use; mood; and new medication usage to monitor potential drug-drug interactions. If the survey is not completed, a reminder will be sent to the participant every 30 minutes for 150 minutes (5 total reminders). Responses will be collected, password-protected, and encrypted locally on smartphones.

Subjects who endorse medication side effects other than nighttime drowsiness will be contacted by the study physician for a review of symptoms and safety. Additionally, if subjects endorse taking new medications, the study physician will review the information and contact the subject if further information is needed. The study physician and PI will utilize Lexicomp to check drug-drug interactions and only interactions of minor severity will be allowed. Those found to have moderate or severe interactions will be withdrawn from the study, consistent with study exclusionary criteria.

Subjects will also be contacted if medication compliance falls below 80% or above 120%. At the final lab visit, subjects will be asked to bring their blister pack with them to verify compliance using the pill count method. Thus, medication compliance is tracked using both daily self-report, pictures, and objective pill count.

Post-Treatment Lab Visits. During the final days of the trial, subjects will return to the lab to repeat the lab protocol. Individuals enrolled in the BRAINS Group will come in for a separate visit to repeat the fMRI. At study conclusion, subjects will be debriefed and provided a list of AUD treatment referrals and resources.

Self-report Data Processing. All measures will be double entered, checked for discrepancies, and cleaned. Analyses will assume that 'missingness' occurred at random, with data imputed when necessary.

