4.0 Eligibility

4.1 Inclusion Criteria

Adults 18-65 years old will be enrolled in this study. Participants will be required to be generally medically and neurologically healthy. They will also be required to meet current DSM-5 diagnosis of moderate to severe AUD and engage in heavy alcohol use defined as drinking ≥ 14 standard drinks per week if male, and ≥ 7 standard drinks per week if female.

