12.0 Statistical Considerations

13.0 Aim 1. Does a single dose of SUV decrease reactivity to U-threat? Hypothesis

1: Relative to PBO, SUV will acutely dampen startle reactivity to U-threat, but not P-threat. We will conduct a multilevel mixed model with startle magnitude as the dependent variable. Startle to U-threat and P-threat will be included as a within-subjects factor, to test for specific changes in U-threat. Time (baseline vs. acute challenge) and treatment arm (SUV vs. PBO) will be included as within-subjects and between-subjects factors, respectively, and we expect a time x treatment arm x task condition interaction on startle. Models will include a random effect for participant.

14.0 Aim 2. Does daily use of SUV decrease reactivity to U-threat? Hypothesis 2a:

4-weeks of SUV will result in greater reductions in reactivity to U-threat compared with PBO, and these changes will be specific to U-threat. Hypothesis 2b: SUV-related change in U-threat reactivity will be greatest amongst those with higher baseline U-threat reactivity. Exploratory Analysis: SUV will similarly result in decreases in aINS and dACC reactivity and connectivity during U-threat relative to PBO, and brain change will correlate with startle change. For H2a, we will conduct a multilevel mixed model that is nearly identical to the model described for H1. However, the time variable will be modeled as baseline vs. post-treatment. For H2b,

we will include baseline startle to U-threat as a predictor in our model and test for a baseline startle by treatment arm interaction. Lastly, for our exploratory fMRI analyses, we will first extract activation and functional connectivity parameter estimates from anatomical aINS and dACC during U-threat (and P-threat) > No-threat contrast maps. fMRI variables will be tested as dependent variables in the model used for H2a. Magnitude of brain change will be directly correlated with magnitude of startle change.

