15.0 Aim 3. Does daily use of SUV change alcohol behavior, and is this change linked to brain-behavior U-threat change? Hypothesis 3a: Daily SUV will result in greater reductions in PHDD and DPDD compared with PBO. **Hypothesis 3b:** SUV-related changes in PHDD and DPDD will be greatest in those with higher U-threat reactivity. **Hypothesis 3c:** In all subjects, changes in brain-behavioral U-threat reactivity will correlate with changes in drinking behavior. For H3a, linear mixed models will be used to assess the impact of treatment arm (SUV vs. PBO) on changes in drinking behavior over the 4-week follow-up period (daily reports). If the assumptions of linear models are violated due to skewed residual errors, we will explore the use of Poisson and negative binomial generalized linear mixed models to model drinking behavior. For H3b, baseline startle potentiation to U-threat (and in secondary models, aINS, dACC, and BNST parameter estimates) will be entered as a covariate/predictor and we will test for a baseline startle to U-threat by treatment arm interaction on drinking behavior outcomes. Lastly, the hypothesis for H3c will be tested using a linear mixed model that includes magnitude of U-threat and P-threat reactivity (startle and brain, separate models), time, and treatment arm as predictors and PHDD and DPDD as the outcomes. We expect a startle by time interaction such that regardless of treatment arm, a change in U-threat reactivity will correspond to a change in drinking behavior.

Sample Size. Our key hypothesis testing involves treatment arm by session interactions on startle eyeblink potentiation. Assuming a medium to large effect size, which is supported by our preliminary data, a sample size of 40 individuals per treatment group would conservatively yield 91% power (a total sample size of 80 individuals). To account for potential screen-fails, participants requesting to drop out of the study, and the PI withdrawing participants due to meeting termination criteria, approval for 120 participants is requested.

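### The models for Aims 1–3 name neither sex, on which randomisation is stratified, nor protocol arm, which it also allocates; some power may be lost where these factors predict the tested outcome or change

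*Combined protocol and SAP*

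**What the plan says.** **Allocation.** Section 6.0 (Randomization, Blinding, and Dosing) states "A computerized stratified block randomization will assign subjects to a treatment group and protocol arm" and then "The randomization will be stratified by biological sex". Sex is the only stratification factor named. The Study Overview in the same section says "participants have a chance of being randomized to four different groups (20 participants/group"), so treatment is crossed with protocol arm in four cells of 20.

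**Models.** In section 12.0, Aim 1 uses time, treatment arm and task condition, and "we expect a time x treatment arm x task condition interaction on startle". It adds: "Models will include a random effect for participant". For H2a, "we will conduct a multilevel mixed model that is nearly identical to the model described for H1", with post-treatment replacing the acute challenge. H2b and H3b add baseline reactivity. H3a applies linear mixed models to daily drinking reports, with Poisson or negative binomial models as a fallback. H3c adds U- and P-threat reactivity. None of these names sex or protocol arm. The only covariates mentioned elsewhere are lifetime psychiatric diagnoses, as candidates (section 6.0, Participants).

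**Powered test.** The Sample Size paragraph says "Our key hypothesis testing involves treatment arm by session interactions on startle eyeblink potentiation" and gives 91% power with 40 per arm.

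**Sex and drinking.** Section 4.1 sets the entry minimum at 14 "standard drinks per week if male" and 7 if female.

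**The concern.** Balancing a factor by design removes its contribution to the true variability of the treatment difference. If the model then omits the factor, its variance stays in the residual. The reported standard error is too wide for that contrast, the test rejects less often than its nominal level, and power is lost.

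Two features make this worth checking:

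- Sex plausibly predicts drinking level, given the different entry floors.
- BRAINS participants do an additional shock-and-startle task between the baseline EMG visit and the acute challenge, so protocol arm could affect change over time as well as level.

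At stake is precision in a trial of 80. The plan also leaves open which covariates will be used.

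**Working it through.** **1. The plan's own figure.** The 91% has no numeric effect size, alpha, sidedness or correlation behind it, so it cannot be reproduced uniquely. For a two-sample t test on per-person change, 40 per arm and two-sided 0.05 (assumed), power is 60% at d = 0.5, 90.5% at d = 0.74, 91% at d = 0.747 and 94% at d = 0.8. So 91% fits d of about 0.75, within a medium-to-large range.

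**2. H1 and H2a: what cancels.** The three-way term compares arms on

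C = (U after − U baseline) − (P after − P baseline).

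- A stable sex or protocol-arm difference enters with weights +1 −1 −1 +1 = 0.
- A factor × time effect enters with +1 (U after) and −1 (P after), also 0.
- Only a factor × time × condition effect remains.

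Numerical check: one simulated data set of 80 people, 2 sessions × 2 conditions, sex effect 1.0 and protocol-arm effect 0.5 on a between-person SD of 1.

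| Term | SE without factors | SE with both main effects |
|---|---|---|
| time × arm × condition | 0.28841 | 0.28841 |
| time × arm | 0.20393 | 0.20393 |
| arm main effect | 0.268 | 0.237 |

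In repeated simulation with a sex effect of 1.0, power for the three-way term was 90.4% with and without adjustment.

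**3. H1 and H2a: what might not cancel.** Section 6.0 gives 24 shocks per EMG task and 20 per run over two fMRI runs, which is 40. Leaving out the shock work-ups:

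| Task shocks received before | BEHAVIOR | BRAINS |
|---|---|---|
| Acute challenge task | 24 | 24 + 40 = 64 |
| Post-treatment EMG task | 24 + 24 = 48 | 24 + 40 + 24 = 88 |

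This difference in exposure arises after baseline, so a participant intercept cannot absorb any effect it has. Whether it has one, and whether that differs between U and P, is not documented. Suppose a balanced two-level factor shifts C by the assumed amount and its interactions with time and condition are modelled (simulated with sex as the factor):

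| Shift in C (SD) | SE without → with | Fall in SE | Power without → with |
|---|---|---|---|
| 0.3 | 0.3155 → 0.3118 | 1% | 89.3 → 89.6% |
| 0.5 | 0.3225 → 0.3124 | 3% | 89.2 → 90.5% |
| 0.8 | 0.3363 → 0.3117 | 7% | 88.2 → 91.6% |

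Time interactions alone do little. In a separate simulation (residual SD 1, sex × time × condition effect 0.8) they moved power only from 88.8% to 89.0%.

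**4. H3a read as a between-person contrast.** Assume equal numbers of each sex, residual SD 1, 40 per arm and two-sided 0.05. The plan gives no drinking effect size, so 0.74 is borrowed from step 1. The adjusted SE is √(2/40) = 0.2236. A sex gap g multiplies the unadjusted reported SE by k = √(1 + g²/4).

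- Variance share: (g²/4)/(1 + g²/4)
- Fall in SE with adjustment: 1 − 1/k
- Unadjusted type I error: 2(1 − Φ(1.96k))
- Unadjusted power: Φ(0.74/0.2236 − 1.96k); adjusted power: Φ(0.74/0.2236 − 1.96) = 91.14%

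| g (assumed) | Variance share | Fall in SE | Type I error | Unadjusted power | Gain (points) |
|---|---|---|---|---|---|
| 0.2 | 1.0% | 0.5% | 0.049 | 90.98% | 0.16 |
| 0.5 | 5.9% | 3.0% | 0.043 | 90.13% | 1.01 |
| 0.8 | 13.8% | 7.2% | 0.035 | 88.46% | 2.68 |

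Simulation with t tests (6,000 trials per case) agrees: 90.1 → 90.3%, 88.9 → 89.9% and 87.6 → 90.7%. With unequal numbers of men and women, g²/4 becomes p(1 − p)g², which is smaller, so the loss shrinks.

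**The case against.** A reader might infer that standard errors are too large and power is lost throughout Aims 1–3. The documents do not support that. The powered startle tests are interactions with time in a model with a participant effect, and step 2 shows that stable differences drop out of them completely. The type I formula in step 4 applies to the variance of the contrast being tested, not to outcome variance in general.

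The case that there is little to fix has further parts that stand:

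- Protocol arm is an allocated factor crossed with treatment, not a stratum. Leaving it out does not bias the drug comparison.
- The 14 and 7 drinks per week are entry floors. They give no variance explained for heavy drinking days or drinks per drinking day. If heavy drinking days are defined separately by sex, which the documents do not say, the gap in that outcome could be smaller.
- H3a concerns change in drinking. If the tested term is arm × time, or a comparison with the Timeline Follow-back taken at Lab Visit 1, stable sex differences largely cancel there too.
- Carry-over from the fMRI session is conjecture. That task uses a different shock site with re-calibrated intensity, and each EMG threat task is preceded by habituation.

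What remains is narrower. The H3a text names no baseline drinking term and does not say which term carries the arm effect, so a between-person reading is open. The additional BRAINS session is also a real difference in procedure after baseline.

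**Conclusion.** The omission is real and the point is minor. For H1 and H2a there is no loss from stable sex or protocol-arm differences. A loss arises only if a factor changes the U-versus-P difference over time, and the documents give no size for that. For H3a and H3b, read as between-person contrasts, the loss is about 0 to 3 points of power at sex gaps of 0.2 to 0.8 SD. Any error is conservative, so a positive result would not be in doubt.

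All sizes rest on assumptions: the gaps themselves, equal numbers of each sex, no dropout, two-sided 0.05, and a linear model. The Poisson and negative binomial fallback was not examined. The documents state no variance explained by either factor, so no single figure can be given.

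**What to change.** Pre-specify in section 12.0:

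- **H3a and H3b:** sex and protocol arm as fixed effects, with factor × time added if the tested term is arm × time. State which term carries the treatment effect.
- **H1 and H2a:** sex and protocol arm, each with its time, condition and time × condition interactions. Main effects, or time interactions alone, do not act on the three-way contrast.

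This needs no new data and no change to randomisation. It costs two degrees of freedom per tested contrast at the person level, and in H1 and H2a eight extra coefficients (four per factor). Stating the covariates in advance also removes a choice that would otherwise be made after the data are seen.
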